8.2.5 Clinical Benefit Rate

Clinical benefit is defined as achieving SD for ≥ 24 weeks or a confirmed, BOR of CR or PR per RECIST 1.1. The proportion of subjects with clinical benefit and the corresponding two-sided, exact Clopper Pearson binomial 95% confidence interval will be calculated for both the ICR and investigator assessments.

8.2.6 Duration of Response

DOR is defined as the time from the first confirmed objective response (CR or PR) to documented PD per RECIST 1.1 or death from any cause. Subjects who are alive and have not progressed at the time of the analysis will be censored at the time of their last tumor assessment that was a CR, PR, SD, or non-CR/non-PD. The same censoring rules outlined in [Table 6](#) for PFS will be applied to DOR with date of first dose replaced by date of first response. DOR will be calculated based on the ICR response assessments and separately for the investigator response assessments. Only subjects who achieve a confirmed objective response will be included in the analysis of each endpoint.

DOR will be analyzed using Kaplan-Meier methodology and a Kaplan-Meier plot of DOR will also be provided. Kaplan-Meier estimates of the quartiles (median, 25th and 75th) will be computed. Two-sided 95% CI for the quartiles using the Brookmeyer and Crowley method (Brookmeyer and Crowley 1982) with log-log transformation (Collett 1994) will be presented. Tumor assessment dates will be imputed as described in [Section 7.3](#). In the event there are too

few confirmed responses to generate Kaplan-Meier estimates, DOR may be summarized descriptively (i.e., mean, median, standard deviation, minimum, and maximum).

The proportion of subjects with a DOR \geq 16 weeks and the corresponding two-sided, exact Clopper Pearson binomial 95% CI will also be calculated. In addition, the Kaplan-Meier probability and corresponding 2-sided 95% CI at Week 16 will be calculated.

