1.5. HER2-targeted Therapies in BTC

Of the HER2-targeted agents, lapatinib has been evaluated in both the first- and second-line setting in an unselected population of subjects with advanced BTC ([Ramanathan 2009](#), [Peck 2012](#)). Results of these studies were unremarkable and showed no significant evidence of anti-tumor activity. However, in a separate case series of 9 GBC and 5 CC subjects treated with trastuzumab, lapatinib, or pertuzumab monotherapy, 4/9 GBC subjects (44.4%) had partial responses (PR) and 1/9 GBC subject (11.1%) had a complete response (CR), equating to an ORR of 55.6% ([Javle 2015](#)). An additional 3 GBC subjects had stable disease (SD). The duration of response (DOR) ranged from 8+ to 168 weeks (median 40 weeks). All 5 GBC subjects with objective responses had HER2 overexpression or amplification. The clinical benefit of HER2-targeted agents may therefore be associated with HER2 amplification or over-expression, and a biomarker-based strategy is needed to select patients for HER2-directed therapies.

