9.4.6. Efficacy Analyses

The endpoints listed below will be evaluated based on both the ICR and the investigator RECIST 1.1 response assessments.

The primary analysis of efficacy will evaluate these endpoints and the primary endpoint, confirmed ORR, for subjects in the Cohort 1 Primary Efficacy Analysis Set. Secondary analyses of these endpoints will evaluate these endpoints for the Cohort 2 Efficacy Analysis Set (see [Section 9.3](#)). If a meaningful treatment effect is observed in Cohort 2, a pooled efficacy analysis of Cohort 1 + 2 may be performed.

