9.4.6.5. Duration of Response

DOR is defined as the time from the first objective response (CR or PR) to documented PD per RECIST 1.1, clinical progression, or death from any cause. Only subjects who achieve a confirmed response in the Safety Analysis Set will be included in the analysis. Details of the censoring scheme for this analysis will be described in the SAP.

Kaplan-Meier plots and estimates of the quartiles and their corresponding 95% CI will be computed.

In addition, the proportion of subjects with a DOR ≥ 16 weeks and the corresponding exact binomial 95% CI will be calculated.

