6.5 Determination of Sample Size

This study will enroll approximately 100 subjects: approximately 75 subjects in Cohort 1 and approximately 25 subjects in Cohort 2. No formal sample size calculations were performed. Approximately 75 subjects will be enrolled in Cohort 1 to evaluate the primary endpoint of confirmed ORR for the primary analysis of efficacy. The 2-sided, exact Clopper Pearson binomial 95% confidence intervals (CIs) that could be observed with this sample size are listed in [Table 1](#). A minimum of 23 subjects with confirmed objective response from a sample-size of 75 would result in the lower bound of a two-sided, exact Clopper Pearson binomial 95% CI exceeding 20 percentage points.

Table 1: Clopper-Pearson 95% Confidence Intervals for N=75 Subjects

Confirmed ORR		95% CI	
Percent	Responses	Lower	Upper
20.0%	15	11.7%	30.8%
25.3%	19	16.0%	36.7%
30.7%	23	20.5%	42.4%
36.0%	27	25.2%	47.9%
40.0%	30	28.9%	52.0%
45.3%	34	33.8%	57.3%
50.7%	38	38.9%	62.4%

Approximately 25 subjects will be enrolled in Cohort 2 to evaluate the primary endpoint of confirmed ORR as a secondary analysis of efficacy. The 2-sided, exact Clopper-Pearson binomial 95% CIs that could be observed with a sample size of 25 subjects are listed in [Table 2](#).

Table 2: Clopper-Pearson 95% Confidence Intervals for N=25 Subjects

Confirmed ORR		95% CI	
Percent	Responses	Lower	Upper
20.0%	5	6.8%	40.7%
24.0%	6	9.4%	45.1%
28.0%	7	12.1%	49.4%
32.0%	8	15.0%	53.5%
36.0%	9	18.0%	57.5%
40.0%	10	21.1%	61.3%
44.0%	11	24.4%	65.1%
48.0%	12	27.8%	68.7%

With a sample size of 100 subjects (Cohorts 1 and 2 combined), the probabilities of detecting 1 or more treatment-emergent adverse events (TEAEs) for various frequencies of occurrence in this population are listed in [Table 3](#).

Table 3: Probabilities of Detecting ≥ 1 Adverse Events

Frequency of Adverse Event	Binomial Probability
0.1%	10%
1%	63%
5%	99%

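### SAP 8.2.6 allows an ordinary mean, median and SD of duration of response when responders are few, with no numeric trigger and no rule for censored durations

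*SAP*

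**What the plan says.** Protocol 9.4.6.5 gives one method for DOR: "Kaplan-Meier plots and estimates of the quartiles and their corresponding 95% CI will be computed". It has no alternative for small numbers.

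SAP 8.2.6 keeps that method: "DOR will be analyzed using Kaplan-Meier methodology and a Kaplan-Meier plot of DOR will also be provided". It treats DOR as right-censored: "Subjects who are alive and have not progressed at the time of the analysis will be censored" at the last adequate tumor assessment, and the Table 6 rules for PFS apply with first response in place of first dose. It then adds an option. If there are too "few confirmed responses to generate Kaplan-Meier estimates, DOR may be summarized descriptively (i.e., mean, median, standard deviation, minimum, and maximum"). The section ends with a further Kaplan-Meier output that has no exception for small sets: "In addition, the Kaplan-Meier probability and corresponding 2-sided 95% CI at Week 16 will be calculated".

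SAP section 9, which records departures from the protocol, lists two changes to DOR: clinical progression is no longer an event, and the response must be confirmed. The descriptive option is not listed.

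The SAP names no cohort for the option. The sets where few responders are possible include Cohort 2 ("approximately 25 subjects in Cohort 2"), for which Protocol 9.4.6 plans DOR among other endpoints: "Secondary analyses of these endpoints will evaluate these endpoints for the Cohort 2 Efficacy Analysis Set". They also include the subgroups of SAP 7.2 and the four China efficacy sets of SAP 8.9.

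**The concern.** A responder who is still in response at the cutoff contributes a lower bound on DOR, not a DOR. Kaplan-Meier uses that bound correctly. An ordinary mean, SD or median has no place for it, so the programmer must either enter the censored time as if the response had ended or leave the subject out. The SAP does not say which, and both shorten DOR.

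The trigger is also unclear. A Kaplan-Meier curve exists for any set with at least one responder, so a literal reading almost never brings the option into play. If 'too few' is instead taken in practice to mean that the median cannot be estimated, the option applies where censoring is heaviest. There, 'not reached' is the right answer.

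At stake is the DOR reported for small sets. Protocol 3.2 gives DOR the job of showing whether the response rate is clinically meaningful. A descriptive DOR for one set would also not be comparable with the Kaplan-Meier DOR for Cohort 1.

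**Working it through.** **Plan's own figure.** None is given for this option, so there is nothing to reproduce.

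**1. What the two methods do with three responders.** Take invented durations of 4, 5+ and 9+ months, with '+' for ongoing.
- Kaplan-Meier: the curve falls to 2/3 at 4 months and stays there. The median is not reached.
- Counting censored times as ended: mean (4 + 5 + 9)/3 = 6; median 5; SD = √[((−2)² + (−1)² + 3²)/2] = √7 = 2.65 months.
- Dropping censored subjects: a single value of 4 months and no SD.

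**2. Size of the bias.** All inputs here are assumptions. True DOR is exponential with median 9.1 months (the figure Protocol 3.2 cites for another agent), so λ = ln 2/9.1 = 0.0762 per month and the true mean is 1/λ = 13.1. Follow-up after response is uniform on [a, b] months. For the observed time X:
- P(X > t) = e^(−λt) for t ≤ a, and e^(−λt)(b − t)/(b − a) for a < t < b. The ordinary median is where this equals 0.5.
- Censored share = (e^(−λa) − e^(−λb))/[λ(b − a)].
- Ordinary mean = (1/λ)(1 − censored share).

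For a = 3 and b = 16, the censored share is (0.7957 − 0.2956)/0.9902 = 0.505 and the mean is 13.13 × 0.495 = 6.5. The median is 5.85, since e^(−0.4456) × 10.15/13 = 0.640 × 0.781 = 0.50.

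| Follow-up (months) | Censored | Mean, counted as ended | Median, counted as ended | Median, censored dropped |
|---|---|---|---|---|
| 1–10 | 67% | 4.3 | 3.9 | 2.5 |
| 3–16 | 51% | 6.5 | 5.9 | 3.8 |
| 4–22 | 40% | 7.9 | 6.8 | 4.7 |
| True value | – | 13.1 | 9.1 | 9.1 |

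With follow-up of 3–16 months, a true median of 5 gives 4.3 (15% low) and a true median of 13 gives 6.7 (48% low).

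**3. Follow-up tied to the planned cutoff.** SAP 6.6 sets the primary analysis about 6 months after the last Cohort 1 enrollment, and scans are every 8 weeks. Assume response at 8 weeks (8/4.345 = 1.84 months) and uniform accrual over 6 to 24 months. Follow-up after response then starts at 6 − 1.84 = 4.16 months and extends over the accrual period. Counting censored times as ended gives:

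| True median | Ordinary median | Shortfall |
|---|---|---|
| 6 | 4.9 to 5.5 | 8% to 19% |
| 9.1 | 5.6 to 7.3 | 20% to 39% |
| 12 | 5.9 to 8.5 | 29% to 51% |

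At a true median of 9.1, 33% to 59% of durations are censored, and dropping them gives a median of 3.0 to 5.3. With three responders, the chance that at least one is censored, 1 − (1 − share)³, is 71% to 93%. Kaplan-Meier reports its median as not reached in 19% to 55% of such samples.

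**4. How often Cohort 2 would have few responders.** The SAP gives no threshold, so take 1 to 4 as an illustration, with Binomial(25, p):

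| True response rate | P(1–4 responders) |
|---|---|
| 5% | 0.715 |
| 10% | 0.830 |
| 15% | 0.665 |
| 20% | 0.417 |
| 30% | 0.090 |

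At 5% there is also a 0.277 chance of no responder, when there is nothing to summarize.

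**The case against.** The strongest reply is that the sentence is optional and would rarely be used. It says 'may'. Its condition is the number of responses, and taken literally that condition is hardly ever met. Kaplan-Meier remains the stated method, and the Week 16 probability is planned regardless. DOR is secondary, no hypothesis is tested, and with one to four responders no summary is precise. All of this stands, and it limits the severity.

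A reader might also infer more than the documents support:
- *That the SAP replaces Kaplan-Meier with raw durations and counts ongoing responses as ended.* It permits a descriptive summary and is silent on how censored times enter. Counting them as ended is one of two simple readings.
- *That this is mainly a Cohort 2 problem.* The SAP does not name Cohort 2. Protocol 3.2 gives reason to expect lower activity there (no responses among 8 subjects without high IHC in a cited study), but the Cohort 2 table in SAP 6.5 displays rates of 20% to 48%, and at 30% few responders are unlikely.
- *That small numbers cause the bias.* The share of censored durations causes it.
- *That the result would measure only follow-up.* With follow-up of 3–16 months, about half of the durations are completed.

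The reach into other small sets is limited too. Subgroups of 5 or fewer may be left out (SAP 7.2), and the China analyses may not appear in the study report, although SAP 8.9 says that they serve a regulatory submission.

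The reply does not rescue the sentence. It names statistics that cannot carry the censoring defined in the same section, and the protocol provides no such option.

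**Conclusion.** Wrong as written, but minor. The problem goes beyond missing detail, because the SAP names an unsuitable method, leaves its trigger and its censoring rule undefined, and does not record the departure from Protocol 9.4.6.5.

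If the option were used with censored times counted as ended, a true median of 9.1 months would appear as about 4 to 7 months; if they were dropped, it would appear shorter still. These sizes rest on an exponential DOR, a median borrowed from another agent and assumed follow-up. The direction does not depend on those choices as long as some responses are ongoing at the cutoff. With a short true DOR or long follow-up the effect is small. The primary response rate and the Week 16 Kaplan-Meier probability are not affected.

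**What to change.** In SAP 8.2.6, delete the sentence that allows the mean, median, SD, minimum and maximum. Replace it with text to this effect: *Kaplan-Meier estimates will be given for every analysis set with at least one confirmed responder; quartiles or limits that cannot be estimated will be shown as not reached or not estimable. For sets with few responders (state the number, for example fewer than 10), individual durations will be listed with censored values marked '+', and the range will carry the same mark.*

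Protocol 1.5 already uses this notation for a cited case series with five responders, whose DOR "ranged from 8+ to 168 weeks (median 40 weeks"). That passage is a model for the display, not another instance of the problem.

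If the sponsor prefers to keep a descriptive summary, the SAP should define its trigger, state how censored durations enter it, and list it in section 9 as a change from the protocol.

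The cost is one sentence in the SAP and one small extra listing. No data collection, sample size or primary analysis changes.

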8.2.7 Overall Survival (OS)

Overall survival (OS) is defined as the time from the first dose of study treatment until the date of death from any cause or date last known alive for those who did not die.

Specifically,

$$\text{OS} = \text{Date of death or date last known alive} - \text{Date of first dose} + 1$$

Subjects alive at the time of analysis will be considered as censored on the date the subject was last known to be alive (i.e., date of last contact). Subjects lacking data beyond the day of first dose will have their survival time censored on the date of first dose (i.e., OS duration of 1 day). Partial or missing dates of death dates and last known alive date will be imputed as described in [Section 7.3.2](#). If resulting imputed death date is on or before last known alive date, then death of death will be set to last known alive date + 1 day. Details of the censoring scheme are described below in [Table 7](#).

Table 7: Censoring and Event Scheme for OS

Scenario	Progression/Censor Date	Outcome
Not known to have died by data cutoff date	Date last known alive	Censored
Death	Death date	Death

Completely imputed dates (e.g., the analysis cut-off date programmatically imputed to replace the missing end date of a dose administration record) will not be used to derive the last known alive date.

Kaplan Meier estimates of the survival curve and quartiles will be calculated. The 2-sided 95% CIs for the quartiles will be calculated using the Brookmeyer and Crowley method (Brookmeyer and Crowley 1982) with log-log transformation ([Collett 1994](#)). Additionally, the probability of survival at timepoints from 3 months to the end of the follow-up period will be reported.

8.3 Analysis of Safety

All analyses of safety will be based on the safety analysis set which includes all safety evaluable Cohort 1 and 2 subjects.

8.3.1 Extent of Exposure

Zanidatamab exposure will be summarized using counts and percentages for categorical variables and summary statistics (mean, median, standard deviation, and range) for continuous variables. The following variables will be summarized.

- Duration of exposure (see [Section 7.7](#) for definition)
- Number of treatment cycles initiated,
- Total number of infusions received,
- Relative dose intensity percent (see [Section 7.7](#) for definition)
- Total cumulative dose received (see [Section 7.7](#) for definition)
- Frequency of missed infusions and associated reasons
- Frequency of dose reductions and associated reasons
- Frequency of interrupted infusions and associated reasons
- Frequency of delayed infusions and reasons

8.3.2 Adverse Events

Definitions

An adverse event (AE) is defined as any untoward medical occurrence in a clinical study subject administered a medicinal product which does not necessarily have a causal relationship with this treatment. All AEs will be coded to standard “preferred terms” and system organ classifications (SOC) using MedDRA. Severity will be graded by study investigators using NCI-CTCAE v5.0.

Treatment Emergent Adverse Events (TEAEs) are defined as AEs with an onset during or after receipt of the first dose of zanidatamab and up to and including 30 days after the last dose.

Summaries

Adverse events will be summarized by preferred term (and SOC, or severity grade where appropriate). Multiple occurrences of the same AE within a subject will be summarized only once at the most severe grade level for the time frame under consideration. For summaries by severity, only the worst grade for an AE will be counted for a particular subject. AEs occurring prior to the first dose of zanidatamab or more than 30 days after the last dose of zanidatamab will be excluded from summaries but included in data listings.

The following summaries will be produced:

- Overall Summary of Adverse Events – Subject Incidence

- Overall Summary of Adverse Events – Event Frequency
- Incidence of Treatment Emergent Adverse Events
- Incidence of Grade 3 and Higher Treatment Emergent Adverse Events
- Incidence of Zanidatamab Related Treatment Emergent Adverse Events
- Incidence of Zanidatamab Related Grade 3 and Higher Treatment Emergent Adverse Events
- Incidence of Treatment Emergent Adverse Events Leading to Discontinuation of zanidatamab
- Incidence of Zanidatamab Related Treatment Emergent Adverse Events Leading to Discontinuation of Zanidatamab
- Incidence of Treatment Emergent Adverse Events Leading to Dose Reduction
- Incidence of Zanidatamab Related Treatment Emergent Adverse Events Leading to Dose Reduction
- Incidence of TEAEs Leading to Dose Delay of Zanidatamab
- Incidence of TEAEs Leading to Dose Interruption of Zanidatamab
- Incidence of Grade 5 TEAE

In addition to summary tables, the following listings will be produced.

- All TEAEs
- All non TEAEs
- AEs Resulting in Death
- AEs Leading to Discontinuation of Zanidatamab
- AEs Leading to Dose Reduction of Zanidatamab
- AEs Leading to Dose Delay of Zanidatamab
- AEs Leading to Infusion Interruption

8.3.3 Serious Adverse Events and Deaths

Serious adverse events (SAEs) will be summarized by preferred term and SOC using counts and percentages. Multiple occurrences of the same SAE within a subject will be counted only once for the timeframe under consideration. The following summaries of SAEs will be produced.

- Incidence by decreasing frequency of preferred term
- Incidence by SOC and decreasing frequency of SOC and preferred term
- Incidence of zanidatamab related SAEs by decreasing frequency of preferred term

In addition to summary tables, listings of SAEs will be produced.

The following summaries of death will be produced.

- A table of death showing cause of death that occurred ≤ 30 days after last dose versus that occurred > 30 days after last dose
A listing of all deaths

8.3.4 Adverse Events of Special Interest and Select Adverse Events

AESIs to be summarized include the following:

- a. **Infusion Related Reactions (IRR):** Defined using the MedDRA preferred term of, “Infusion Related Reaction” or identified by the investigator as an infusion related reaction.
- b. **Non-infectious Pulmonary toxicities:** Defined as events in the Broad Interstitial Lung Disease SMQ.
- c. **Potential Cardiac events:** Defined as grade 2 or higher adverse events in the Broad Cardiac Failure SMQ or ECHO/MUGA scan results that indicate a post baseline decrease in LVEF of ≥ 10 percentage points from pretreatment baseline and a value $< 50\%$.
- d. **Confirmed cardiac events:** Defined as the subset of potential cardiac events (bullet c. above), that have been clinically reviewed by Zymeworks and determined to be consistent with cardiac events of absolute decrease in LVEF of ≥ 10 percentage points from pretreatment baseline and a value $< 50\%$, and/or grade ≥ 2 heart failure.

Select AEs to be summarized include the following:

- **Treatment-emergent diarrhea:** Defined using the MedDRA preferred term of “Diarrhoea”
- **Treatment-emergent embryo-fetal toxicity:** Defined using the modified Pregnancy and neonatal topics SMQ which excludes *the sub SMQ Lactation related topics including neonatal exposure through breast milk (SMQ)*.

Adverse events of special interest (AESIs) may be listed and summarized by MedDRA preferred term using counts and percentages. Multiple occurrences of the same AESI within a subject will be counted only once for the time frame under consideration. For summaries by severity, only the worst grade for an AESI will be counted for a particular subject. If 5 or fewer subjects have a particular AESI/Select AE, a data listing will be provided in lieu of a summary table.

The time to first onset and duration will be calculated and summarized for each AESI and Select AE. For a particular AESI/Select AE, the time to first onset for a subject is defined as either:

- Date of 1st occurrence – date of 1st infusion (C1D1) + 1 day

Or

- Date and time of 1st occurrence – date and time of 1st infusion + 1 min

The formula used above will depend on the unit of time used in the data collection for the event.

Time to first onset will be summarized using summary statistics (n, mean, median, standard deviation, range).

Time to resolution of AESI/Select AEs will be summarized for events that have an AE end date. Estimates of median, minimum and maximum time to resolution will be provided using descriptive statistics. Time to resolution is defined as the time from the start of the AE to the end date of the AE. The number and percentage of events without resolution will also be provided.

a.

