7.8.1.3. Reporting Periods for Adverse Events and Serious Adverse Events

The safety reporting period for all AEs and SAEs is from the start of study drug dosing on Cycle 1 Day 1 to 30 days after the last dose of study drug. However, all study protocol-related SAEs are to be recorded from the time of signing the pre-screening or main informed consent for the study. All SAEs that occur after the safety reporting period and are considered related to prior zanidatamab study drug treatment in the opinion of the investigator should also be reported to the sponsor.

All AEs (including SAEs and AESIs) will be followed until significant changes return to baseline, the event stabilizes (recovering/resolving) or is no longer considered clinically significant by the investigator, or the subject dies, is lost to follow-up, or withdraws consent, or study closure.

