6.6 Timing of Analyses and Interim Analyses

No interim analyses of the efficacy will be performed for this study. The primary analysis of efficacy will be performed approximately 6 months after the last subject has been enrolled into Cohort 1.

Safety and study conduct will be monitored throughout the study by an independent data monitoring committee (IDMC). The committee is tasked with monitoring the safety of participants in this study through regular and/or ad hoc meetings. The first IDMC meeting will be held after the first 25 subjects have received at least 1 dose of study treatment; subsequent meetings will be held quarterly to review cumulative safety data to identify any potential new safety signals. Additional IDMC meetings will be held at least 28 days after the tenth subject enrolled in China has received 1 dose of zanidatamab to review safety. The IDMC will be responsible for making recommendations to the sponsor as to appropriate study direction; further details will be provided in the IDMC charter.

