7.3.4.2 Adverse Event End Dates

Missing or partially missing end dates for AE which are known to have resolved will be imputed as follows:

- Missing day only: The day will be imputed as last day of the month (e.g., 31-*MMM*-*YY* or 30-*MMM*-*YY*). The AE end date is then imputed as the minimum of {last day of the month} and {death date}. If the month and year are the same as the data cutoff date month and year, then the data cutoff date will be used as the imputed AE end date.

- Missing month and day: The missing month and missing day will be imputed as December 31. The AE end date is then imputed as the minimum of {Dec 31 of the year}, {death date}, {End of Study date} and {data cutoff date}.
- Missing month, day, and year: The AE end date will be imputed as the minimum of {death date}, {End of Study date} and {data cutoff date}.

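### Time to resolution of AESIs and select AEs is summarised only for events with an end date, so its median runs short wherever events are still open

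*SAP*

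**What the plan says.** SAP 8.3.4 sets out the summary in four sentences.

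- Which events count: "Time to resolution of AESI/Select AEs will be summarized for events that have an AE end date".
- The statistics: "Estimates of median, minimum and maximum time to resolution will be provided using descriptive statistics".
- The definition: "Time to resolution is defined as the time from the start of the AE to the end date of the AE".
- The remainder: "The number and percentage of events without resolution will also be provided".

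The same section replaces the table with a listing when 5 or fewer subjects have a given AESI or select AE.

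SAP 7.3.4.2 limits end-date imputation to resolved events: "Missing or partially missing end dates for AE which are known to have resolved will be imputed as follows". An ongoing event therefore gets no end date and does not enter the summary by that route.

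Protocol 7.8.1.3 has all AEs followed until they return to baseline, stabilise or are no longer clinically significant, "or the subject dies, is lost to follow-up, or withdraws consent, or study closure". Follow-up can thus stop while an event is open.

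On timing, SAP 6.6 says: "The primary analysis of efficacy will be performed approximately 6 months after the last subject has been enrolled into Cohort 1". That sentence concerns efficacy, but a safety summary at the same cutoff would also catch some events before they resolve.

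**The concern.** A duration is seen in full only if the event ends before observation does. At a given length of follow-up after onset, a long event is more likely than a short one to be open, so keeping only completed events over-represents short ones. The resulting median is a correct description of the events that resolved. It is too short as an answer to how long such an event lasts once it starts, which is how a recovery time in a safety section is usually read.

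What is at stake is the reported recovery time for the AESIs and for diarrhea. The protocol's history of changes gives accurate information on duration, reversibility and resolution as the reason for following all AEs alike. A median over resolved events only does not fully serve that aim.

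**Working it through.** The documents state no time to resolution and no unresolved share, so there is no figure of the plan to reproduce. The direction follows from the rule. The size below rests on assumptions.

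**Simplest case.** Let resolution time T be exponential and censoring time C be independent and exponential. Given T ≤ C, T is exponential with the summed rate. With u the unresolved share, the resolved-only median is the true median × (1 − u). At u = 10% it is 10% short; at u = 30% it is 30% short.

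**Limited follow-up after onset.** Assume T is exponential with median 28 days, so λ = ln 2 / 28 = 0.02476 per day, and C is uniform on 0 to c days.

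- Unresolved share: u = (1 − e^(−λc)) / (λc).
- The resolved-only median m solves (1 − e^(−λm)) − [1 − (1 + λm)e^(−λm)] / (λc) = (1 − u)/2.

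Example with c = 182: λc = 4.505, so u = (1 − 0.0110)/4.505 = 0.2195 and the right side is 0.390. At m = 21.5, λm = 0.532 and e^(−λm) = 0.587. The left side is 0.413 − 0.101/4.505 = 0.390, so m is about 21.5 days, 23% short.

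| c (days) | unresolved | resolved-only median (days) | short by |
|---|---|---|---|
| 808 | 5% | 26.6 | 5% |
| 540 | 7% | 25.9 | 8% |
| 365 | 11% | 24.8 | 11.5% |
| 182 | 22% | 21.5 | 23% |
| 120 | 32% | 18.4 | 34% |
| 84 | 42% | 15.4 | 45% |

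The last three rows cap follow-up after onset at about 3 to 6 months for everyone.

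**Shape of the distribution.** Simulated Weibull resolution times (true median 14 days, shape 0.7 to 1.5, exponential censoring) gave these ratios of resolved-only to true median: 0.91 to 0.97 at 5% unresolved, 0.84 to 0.95 at 10%, 0.69 to 0.89 at 20% and 0.55 to 0.83 at 30%. The Kaplan-Meier median over all events was 13.9 to 14.1 days throughout.

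**Speed of resolution.** With exponential resolution and follow-up after onset assumed uniform on 14 to 540 days:

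| true median (days) | unresolved | resolved-only median (days) |
|---|---|---|
| 1 | 0% | 1.0 |
| 30 | 6% | 27.7 |
| 90 | 22% | 68 |
| 180 | 41% | 99 |

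**A rule that pulls the other way.** For resolved events with a fully missing end date, SAP 7.3.4.2 takes the earliest of death, end of study and data cutoff, which can lengthen the duration. In the 14-day exponential case with 20% unresolved, the resolved-only median is 11.2 days. Placing 10% of resolved events at an assumed 300 days raises it to 13.1; placing 20% there raises it to 15.9, above the true value. This offset would be accidental and needs such dates to be common.

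**The case against.** The strongest reply is that the SAP says what it does. It names the restricted set, calls the result descriptive and reports the unresolved number and percentage. On that reading it is a valid conditional summary, and only a table label is missing. This stands in part: nothing is concealed, and the figure is correct for resolved events. But disclosure does not give the reader an all-event recovery time, and no other analysis in the section does.

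A reader might infer several stronger things that the documents do not support.

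- *That early discontinuation makes open events common.* Stopping treatment does not end AE follow-up under Protocol 7.8.1.3. Death can: the randomised second-line chemotherapy trial cited in Protocol 1.2 had median survival of 6.2 and 5.3 months in its two arms. No unresolved share for this trial follows from that.
- *That 23 to 45% is the expected size.* It requires the short follow-up caps shown above. Earlier enrolled subjects have longer potential follow-up than the last, and windows of 0 to 365 or 0 to 540 days give about 8 to 12%.
- *That the omitted events are the longest.* An event starting just before cutoff is open whatever its length. Long events are only over-represented.
- *That every AESI is affected.* If infusion reactions resolve within days, the effect vanishes.
- *That cardiac events will certainly show it.* The Phase 1 data in Protocol 1.6 report no treatment-related LVEF decrease of 10% or more among 58 subjects. If 5 or fewer subjects have the event here, the listing rule leaves no median to distort.

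**Conclusion.** The point holds in a limited form. Wherever a table is produced and some events are unresolved, the planned median understates time to resolution across all events and the maximum ignores longer open ones, unless late imputation of missing end dates happens to offset this. The direction needs only that longer events are more likely to be open. The size depends on the unresolved share, which is unknown: roughly 5 to 12% at 5 to 11% unresolved and 23 to 45% at 22 to 42%, given exponential resolution, a 28-day median and uniform censoring. Slower events reported in more than 5 subjects carry the issue. Severity is minor: no hypothesis, endpoint definition or decision rule depends on this figure.

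**What to change.** In SAP 8.3.4, add for each AESI and select AE type an estimate over all events:

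- Censor unresolved events at the earlier of last AE follow-up and data cutoff.
- Treat death without resolution as a competing event and report the cumulative incidence of resolution. If Kaplan-Meier with censoring at death is preferred, say so, because it treats subjects who died as if they could still have recovered.
- Use the first event per subject, or state how repeat events within a subject are handled.
- Keep the planned median, minimum and maximum, labelled as being among resolved events, next to the unresolved count.

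The cost is SAP wording and a little programming on data already collected. The SAP already uses Kaplan-Meier with censoring for PFS, DOR and OS; cumulative incidence is a small addition. The downside is that the median may look less favourable, or may not be estimable when many events are open. In that case, the proportion resolved by fixed times can be reported instead.
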